### **12.2 Retention of Records**

The Investigator/trial staff must maintain adequate and accurate records to enable the conduct of the trial to be fully documented and the trial data to be subsequently verified. All essential documents, as listed in ICH GCP guidelines, will be retained by the Investigator for at least 2 years after the date the last marketing application is approved for the drug in the indication being investigated and until there are no pending or contemplated marketing applications; or, if no application is to be filed or if the application is not approved for such indication, until 2 years after formal discontinuation of clinical development of the drug.

The Investigator must notify and obtain written approval from BN before destroying any clinical trial documents or images (e.g., scan, radiograph, ECG tracing) at any time. The Sponsor will inform the Investigator of the date that the trial records may be destroyed or returned to BN.

Should an Investigator wish to assign trial records to another party, advance written notice will be given to the Sponsor. BN must also be notified in advance and provide express written approval of any change in the maintenance of clinical trial documents, should the Investigator choose to move trial records to another location.

If the Investigator cannot guarantee the aforementioned archiving requirements at the clinical trial site for all such documents, special arrangements must be made between the Investigator and BN to store these documents in secure sealed containers away from the clinical trial site. These documents must be able to be returned in their secure sealed containers to the clinical trial site for auditing purposes.

### **13 Monitoring of the Trial**

Representatives of BN or its designee (e.g., CRO) will monitor this trial until completion. Monitoring will be conducted according to the monitoring plan which must be approved by BN. The monitoring plan will specify in detail the items for source data verification and other tasks, to be performed by the CRA during the clinical trial site visit.

Monitoring will be conducted through personal visits with the Investigator and site staff, remote monitoring, as well as any appropriate communications by mail, fax, email, or telephone. The purpose of monitoring is to ensure that the trial is conducted in compliance with the protocol, SOPs, and other written instructions and regulatory guidelines, and to ensure the quality and integrity of the data. This trial is also subject to reviews or audits.

To assure the accuracy of data collected in the eCRFs, it is mandatory that the monitor have access to all original source documents, including all electronic medical records (EMR) at reasonable times and upon reasonable notice. During the review of source documents, every effort will be made to maintain the anonymity and confidentiality of all subjects during this clinical trial.

### **14 Audits and Inspections**

Site audits may be carried out at any time during or after completion of this trial by the Quality Assurance Department at Bavarian Nordic or designee. All trial-related documentation must be made available to the designated auditor. The Investigator agrees to allow the IRB, representatives of BN, its designated agents and authorized employees from local, state, or Regulatory Authority (e.g., FDA) to inspect the facilities used in this clinical trial at any time before, during, or after completion of the clinical trial and, for purposes of verification, allow direct access to the hospital or clinic records of all enrolled subjects. A statement to this effect will be included in the informed consent and permission form authorizing the use of protected health information. In the event of such an inspection, BN will be available to assist in the preparation. All pertinent trial data should be made available as requested for verification, audit, or inspection purposes.

## 15 Responsibility of the Investigators

The Principal Investigator (PI) agrees to carry out the trial in accordance with the guidelines and procedures outlined in this clinical trial protocol. The PI especially consents to strictly adhere to the ethical principles mentioned in [Section 10.1](#) of this protocol.

Changes to the protocol require a written Protocol Amendment to be submitted and approved by the local IRB, the Coordinating Investigator and the PI of the respective clinical trial site. Changes are allowed only if the trial value is not reduced and if they are ethically justifiable. The amendment must be passed on to all participating investigators with the obligation to adhere to its provisions. If warranted, the subject information has to be changed accordingly.

It is within the responsibility of the investigator that the CRF has to be completed in a timely manner after each subject visit and signed after the subject has finished the trial for each subject participating in the trial.

At the conclusion of the trial, the investigator will return all partly used, unused and empty vaccine containers to the Sponsor or the vaccine containers will be destroyed at the clinical trial site according to local legal requirements.

The investigator may ask to terminate the trial due to administrative or other reasons. If this should be the case, appropriate measures which safeguard the interests of the participating subjects must be taken after verification and consultation with the PI.

Each investigator will maintain appropriate medical and research records for this trial, in compliance with ICH GCP (E6), Section 4.9, and regulatory and institutional requirements for the protection of confidentiality of subjects. He/she will permit authorized representatives of the Sponsor and regulatory agencies to review (and, when required by applicable law, to copy) clinical records for the purposes of quality assurance reviews, audits, and evaluation of the trial safety and progress.

The PI agrees to follow the detailed publication policy included in the clinical trial agreement.

By signing this protocol, the PI confirms that he/she has read the entire clinical trial protocol, agrees to its procedures, and will comply strictly with the formulated guidelines.

## 17 Appendices

### 17.1 Appendix 1: Contraception Eligibility Criteria for Female and Male Subjects

A woman is considered of childbearing potential unless post-menopausal (defined as  $\geq 12$  months without a menstrual period) or surgically sterilized. A female subject is eligible to participate if she is not pregnant (as confirmed by a negative  $\beta$ hCG test), not lactating, and at least one of the following conditions applies:

#### **HIGHLY EFFECTIVE METHODS OF CONTRACEPTION**

Hormonal methods of contraception including combined oral contraceptive pills, vaginal ring, injectables, implants and intrauterine devices (IUDs) such as Mirena® by WOCBP subject or male subject's WOCBP partner. Female partners of male subjects participating in this trial may use hormone based contraceptives as one of the acceptable methods of contraception since they will not be receiving study drug

Nonhormonal IUDs, such as ParaGard®

Tubal ligation

Vasectomy

Complete Abstinence\*

\*Complete abstinence is defined as complete avoidance of heterosexual intercourse and is an acceptable form of contraception for all study drugs. Subjects who choose complete abstinence are not required to use a second method of contraception, but female subjects must continue to have pregnancy tests. Acceptable alternate methods of highly effective contraception must be discussed in the event that the subject chooses to forego complete abstinence.

#### **LESS EFFECTIVE METHODS OF CONTRACEPTION**

Diaphragm with spermicide

Cervical cap with spermicide

Vaginal sponge

Male condoms with spermicide

Male Condom without spermicide

Progestin only pills by WOCBP subject or male subject's WOCBP partner

Female Condom\*\*

\*\* A male and female condom must not be used together

## **17.2 Appendix 2: NCI Common Terminology Criteria For Adverse Events (NCI CTCAE version 5).**

[figure not shown]
A copy of the CTCAE version 5 can be downloaded from the NCI website at:

[https://ctep.cancer.gov/protocolDevelopment/electronic\\_applications/docs/CTCAE\\_v5\\_Quick\\_Reference\\_5x7.pdf](https://ctep.cancer.gov/protocolDevelopment/electronic_applications/docs/CTCAE_v5_Quick_Reference_5x7.pdf)

Should a subject experience any AE not listed in the CTCAE version 5, the following grading system should be used to assess severity:

- |         |   |
|---------|---|
| Grade 1 | Mild; asymptomatic or mild symptoms; clinical or diagnostic observations only; intervention not indicated.                          |
| Grade 2 | Moderate; minimal, local or noninvasive intervention indicated.   |
| Grade 3 | Severe or medically significant but not immediately life-threatening; hospitalization or prolongation of hospitalization indicated. |
| Grade 4 | Life-threatening consequences; urgent intervention indicated.   |
| Grade 5 | Death related to AE.  |

### 17.3 Appendix 3: Algorithm for Reporting of AESIs

## 17.4 Appendix 4: RECIST 1.1 Criteria

The best overall response is the best response recorded from the start of treatment until disease progression/recurrence, taking as reference for progressive disease the smallest measurements recorded since treatment started. The patient's best response assignment will depend on the achievement of both measurement and confirmation criteria.

Target Lesions	Non-target Lesions	New Lesions*	Overall Response	Best Overall Response when confirmation is required
CR	CR	No	CR	> 4 week confirmation**
CR	Non-CR/non-PD	No	PR	> 4 week confirmation**
CR	Not evaluated	No	PR	> 4 week confirmation**
PR	Non-CR/non-PD/not evaluated	No	PR	> 4 week confirmation**
SD	Non-CR/non-PD/not evaluated	No	SD	Documented at least once 4 weeks from baseline**
PD	Any	Yes or no	PD	No prior SD, PR, or CR
Any	PD***	Yes or no	PD	No prior SD, PR, or CR
Any	Any	Yes	PD	No prior SD, PR, or CR

\*See RECIST 1.1 Manuscript for further details on what is evidence of new lesions.

\*\*Only for non-randomized trials with response as primary endpoint

\*\*\*In exceptional circumstances, unequivocal progression in non-target lesions may be accepted as disease progression.

Confirmation: To be assigned a status of PR or CR, changes in tumor measurements must be confirmed by repeat assessments that should be performed at least 4 weeks after the criteria for response are first met.

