Exploratory objectives	Analysis of biopsy tissue for differences between pre- and post-treatment samples correlation to patient survival e.g.: 

• T cell receptor (TCR) clonality

• Tumor-Infiltrating-Lymphocytes (TILs)

• Protein expression for e.g. Programmed Death Ligand 1 (PD-L1) and other biomarkers

• Gene expression profiling for molecular subtyping

 Analysis of tumor DNA for Tumor mutational burden; DNA damage response gene mutations, MSI status, MMR deficiency status  Analysis of peripheral blood mononuclear cells (PBMCs) / serum for differences between pre- and post-treatment samples correlation to patient survival e.g.: 

• Antigen-specific immune responses to carcinoembryonic antigen (CEA) and mucin-1 (MUC-1) as well as to other tumor-associated antigens (TAAs) to assess antigen cascade

• Immunophenotyping of immune cell subsets by flow cytometry

• Soluble biomarkers (e.g. cytokines and classical tumor markers)

• TCR clonality

• PD-1/L1 staining

Primary endpoint	Proportion of subjects with a confirmed OR (CR+PR) as per investigator assessment according to RECIST 1.1.

---

Secondary endpoints	
Safety of the combined treatment as measured by:
 

• Adverse Events (incidence, severity, and seriousness of treatment emergent adverse events [TEAEs])

• Laboratory Measures (summaries and shifts from baseline)

• Vital Signs (summaries)

 
OS defined as the time from start of treatment to the time of death from any cause.
 
Duration of response defined as the time from the initial occurrence of documented complete response (CR) or partial response (PR) (whichever occurred first) until documented disease progression or death due to any cause on trial, whichever occurred first.
 
PFS defined as the time from start of treatment to the first event of death or progressive disease (PD) per RECIST 1.1.
 
Percentage of participants with OS and PFS at 6 (PFS only), 9 (PFS only), 12, 18 and 24 months.
 
Immune-related Response Criteria assessment of response rate per iRECIST, delayed responses (pseudo-progressions), duration of response and PFS.

Trial design	Phase 2, Multicenter, Single-Arm, 2 Cohorts, Two-stage

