- Subjects who are discontinued from treatment in the absence of disease progression (e.g., subjects removed for unacceptable toxicity or subject/investigator discretion) should undergo repeat imaging and tumor response assessments until disease progression is documented. Radiological assessment should be continually performed as per schedule. It is recommended that subsequent therapy not be instituted until disease progression is documented.

If the subject is unwilling or unable to come to the clinic for a final EOT assessment, all efforts by the investigator and/or site staff to contact the subject need to be fully documented in the Investigator Site File and the End of Treatment eCRF page, as instructed. Subjects that are withdrawn from treatment will enter the LTFU period.

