4.3.3 Data Handling Conventions for Efficacy Analyses

Subjects who have no record of CR/PR and withdraw early from the trial or are lost to follow up will be considered as non-responders for the ORR analyses.

For PFS, if a subject has no date of death and has not progressed by the time of the analysis, the subject will be censored at the last radiologic assessment showing no progression has occurred. For sensitivity analyses on the FAS, if a subject has no post-baseline radiologic assessment, they will be censored on Day 1.

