4.4.5 Efficacy Analyses

4.4.5.1 Primary Endpoint

The primary efficacy endpoint for the trial is the ORR, defined as the proportion of subjects achieving CR or PR, whichever occurs first, based on investigator-assessed RECIST v1.1 evaluations. Due to the Simon's 2-stage design, hypothesis testing will occur at the end of Stage 1 (interim analysis), and if successful, at the end of Stage 2 within each cohort.

The success criteria are based on the point estimate of the FAS within each cohort. For Cohort 1, at least 4 responses are required in the first 14 subjects to move to Stage 2. For the final Cohort 1 analysis, the null hypothesis that ORR is no more than 0.23 will be rejected if 13 or more responses are observed in the 33 subjects of the FAS. For Cohort 2, at least 3 responses are required in the first 13 subjects to move to Stage 2. For the final Cohort 2 analysis, the null hypothesis that the ORR is no more than 0.15 will be rejected if 10 or more responses are observed in the 35 subjects of the FAS.

In case the number of subjects in the analysis set(s) exceeds the planned sample size, the success criteria will be chosen to preserve the design type I error rate of 0.025 (one-sided) using the exact 2-stage binomial calculation (replacing p with p_0 in formula [1], [Section 2.6.4.2](#)). Type I error equals 1 minus the result from formula [1] when $p = p_0$.

For the final trial analysis, the number and percentage of subjects in each RECIST v1.1 response category, as well as those with a best objective response of CR or PR, will be summarized based on the FAS. The two-sided 90% exact binomial confidence interval for the ORR will be calculated using the Clopper-Pearson method.

Sensitivity analyses will be explored at the end of the trial based on a repeated analysis for any potential immune-related responses observed, as well as a repeat of the analysis on the EE set. For immune-related response cases, ORR analyses using iRECIST criteria will also be provided. For iRECIST, complete or partial responses are still able to be achieved after an initial unconfirmed progression, whereas with RECIST v1.1 once any evidence of progression is recorded, no further responses can be evaluated. For subjects who are not evaluated by iRECIST criteria, their tumor response based on RECIST v1.1 response guidelines will be used.

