4.4.5.2 Secondary Endpoints

4.4.5.2.1 Progression-Free Survival

PFS is defined as the time interval from first treatment to objective tumor progression or death. Accordingly, the precise definition of progression and the timing of CT scans to document progression are very important. Every effort must be made to assure that timeframes for post-treatment CT scans are achieved, so that both treatment groups can be usefully compared.

Assessments must be adequate to evaluate target lesions, non-target lesions, and to search for new lesions.

The secondary endpoint of PFS will be based on the investigator's assessment using RECIST v1.1 response guidelines. PFS will be defined as the time from the day of first treatment to the start of disease progression or death (any cause), whichever occurs first. Subjects who do not have disease progression or have not died will be censored at the date when the last tumor assessment determines a lack of progression. If a subject begins a new anti-cancer therapy or has radiotherapy or surgery at a lesion site prior to documented progression (or death), the subject will be censored at the last assessment where the subject was documented as progression free prior to the intervention.

The Kaplan-Meier curve for PFS and the median PFS will be presented for the FAS.

Additionally, an investigator assessed PFS analysis that includes both investigator-judged PD according to RECIST v1.1 and symptomatic deterioration will be provided.

A binary endpoint for PFS will also be analyzed at milestone time points. The number and percentage of subjects who are progression free based on the above definition at 6, 9, 12, 18, and 24 months will be summarized within the FAS. The two-sided 90% exact binomial confidence interval for the PFS at each time point will be calculated using the Clopper-Pearson method.

A recently published meta-analysis concluded that in checkpoint inhibitor trials 6-month PFS rate is recommended as an endpoint because it is the best predictor of 12-month OS rate. In the absence of prospective validation, the decision adopted is to retain 6-month PFS rate as a secondary endpoint with the aim of complement the primary endpoint ORR in the interpretation of trial results as a whole.

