4.4.5.2.3 Duration of Response

Duration of response is defined as the time from response (CR or PR, whichever occurs first) to investigator assessed progression using RECIST v1.1 or death, and will be summarized based on the number of subjects with response in the FAS. Subjects who do not have disease progression or have not died will be censored at the date when the last tumor assessment determines a lack of progression.

Duration of response will be summarized using the product-limit estimate of median survival along with its 90% confidence interval. The Kaplan-Meier curve will summarize duration of response graphically.

In case some additional immune-related responders are observed, duration of response analyses using iRECIST criteria will be provided. For subjects who are not evaluated by iRECIST criteria, their tumor response based on RECIST v1.1 response guidelines will be used.

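### Best overall response has no cut-off at new anti-cancer therapy, so a response first reached after a switch before progression counts towards the primary ORR

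*Protocol*

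**What the plan says.** **Primary endpoint.** The Protocol Synopsis (1.4) defines it as "Proportion of subjects with a confirmed OR (CR+PR) as per investigator assessment according to RECIST 1.1". SAP 4.4.5.1 describes ORR as "defined as the proportion of subjects achieving CR or PR, whichever occurs first, based on investigator-assessed RECIST v1.1 evaluations". Protocol Appendix 4 (17.4) sets the window: "The best overall response is the best response recorded from the start of treatment until disease progression/recurrence". It requires confirmation at least 4 weeks after the response criteria are first met. Protocol 9.7.1 and SAP 4.4.5.1 also rule out RECIST 1.1 responses after any progression. No ORR text names another end to the window.

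**ORR data handling.** SAP 4.3.3 has one rule: "Subjects who have no record of CR/PR and withdraw early from the trial or are lost to follow up will be considered as non-responders". Under the SAP's General Definitions, a subject who stops treatment early can still complete the trial, so stopping trial product does not trigger this rule.

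**After stopping without progression.** Protocol 4.2.5.1 says these subjects "should undergo repeat imaging and tumor response assessments until disease progression is documented". On the next treatment it says: "It is recommended that subsequent therapy not be instituted until disease progression is documented".

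**PFS.** Protocol 9.7.2.1 and SAP 4.4.5.2.1 do have a cut-off. It begins "If a subject begins a new anti-cancer therapy or has radiotherapy or surgery at a lesion site prior to documented progression (or death" and censors the subject at the last progression-free assessment before the intervention.

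**Duration of response.** SAP 4.4.5.2.3 starts its censoring rule with "Subjects who do not have disease progression or have not died will be censored at the date when the last tumor assessment" and, like ORR, has no new-therapy rule.

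**The concern.** The plan sees that a switch of therapy spoils attribution for PFS but says nothing about it for the primary endpoint. Take a subject with stable disease at Week 10 who stops for toxicity, starts another systemic therapy at Week 14, and has a partial response at Week 22 that holds at Week 28. For PFS this subject is censored at Week 10. For ORR the subject is a confirmed responder.

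Each cohort is tested against a fixed atezolizumab-alone rate (23% and 15%) with no concurrent control. A response to a later drug or to local treatment is therefore credited to CV301 plus atezolizumab. Within this trial the omission can only add to the response count. The trial is open-label with investigator-assessed response, so the classification should not be left to judgement after the data are seen.

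**Working it through.** **1. Reproduce the design.** Inputs are from Protocol 1.4 and 9.7.1. With n1 first-stage subjects, stop if responses are r1 or fewer; declare success at r or more of n:

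P(success | p) = Σ over x > r1 of b(x; n1, p) × P(Bin(n − n1, p) ≥ r − x)

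| | n1, r1, n, r | p0 | type I error (stated) | p1 | power (stated) |
|---|---|---|---|---|---|
| Cohort 1 | 14, 3, 33, 13 | 0.23 | 0.02437 (0.0244) | 0.43 | 0.70266 (0.7027) |
| Cohort 2 | 13, 2, 35, 10 | 0.15 | 0.02494 (0.0249) | 0.33 | 0.70918 (0.7092) |

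Trial-wide: 1 − (1 − 0.02437)(1 − 0.02494) = 0.0487. The plan gives about 4.7% from simulation and a limit of 0.05 (Protocol 9.10, SAP 4.4.4), so there is little room to spare.

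**2. Add post-switch responses under the null.** Let s be the share of non-responders who switch before progression and q the share of those who respond to the next therapy. The counted null rate is p0 + (1 − p0) × s × q.

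The documents give neither quantity for this trial. As anchors from Protocol 2.1:
- q: 11.4% and 13.4%, the chemotherapy response rates reported for post-platinum patients in the two phase 3 trials described there. Using them in Cohort 1 is an extrapolation.
- s: 5% and 8%, the pembrolizumab discontinuation and atezolizumab withdrawal figures for first-line patients. The atezolizumab sentence also gives 34% for treatment discontinuation; I read the 8% as permanent stopping. Not everyone who stops would switch before progression, and some stop for reasons other than toxicity, so s remains an assumption.

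| s, q | s × q | Cohort 1 counted null | type I error | Cohort 2 counted null | type I error | trial-wide |
|---|---|---|---|---|---|---|
| 0 | 0 | 0.2300 | 0.0244 | 0.1500 | 0.0249 | 0.0487 |
| 5%, 11.4% | 0.0057 | 0.23 + 0.77 × 0.0057 = 0.2344 | 0.028 | 0.15 + 0.85 × 0.0057 = 0.1548 | 0.030 | 0.058 |
| 8%, 13.4% | 0.0107 | 0.23 + 0.77 × 0.0107 = 0.2383 | 0.032 | 0.15 + 0.85 × 0.0107 = 0.1591 | 0.036 | 0.067 |

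Expected miscounted responses, n × (1 − p0) × s × q, are 0.15–0.27 in Cohort 1 and 0.17–0.32 in Cohort 2.

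**3. Stage 1.** The table counts post-switch responses at both stages. SAP 2.6.4.1 runs the Stage 1 analysis once the first 14 (or 13) subjects have two post-baseline scans, at about Weeks 10 and 22. Unless the switch came before the Week 10 scan, a post-switch response on scheduled scans appears at Week 22 at the earliest and is confirmed at Week 28. It then counts at Stage 1 only if the analysis runs late enough. If post-switch responses are excluded from Stage 1 altogether and counted only at the final test, type I error is 0.028–0.031 in Cohort 1, 0.030–0.034 in Cohort 2 and 0.057–0.064 trial-wide. The effect is mainly on the final test.

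**4. Weight of one response.** At the final boundary, 12/33 (36.4%) becomes 13/33 (39.4%) and 9/35 (25.7%) becomes 10/35 (28.6%). Either change turns failure into success.

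**The case against.** The strongest reply is that the documents nowhere say such a response counts, and that several provisions work against its occurring. Protocol 8.2.2.2 prohibits other anti-cancer therapy throughout the trial. Protocol 4.2.5.1 makes starting it a reason to stop trial product and advises waiting for progression. The palliative radiotherapy listed as permitted in Protocol 8.2.2.1 is to bone or non-target lesions and is completed before Screening imaging, so an irradiated, shrinking target lesion falls outside it. SAP 4.4.7.9 classifies post-treatment therapies by line and type and plans analyses alongside efficacy, so switchers would be identifiable. Post-progression responses are already excluded, and confirmation is required.

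All of this stands, and it makes the event uncommon and visible. It does not remove the gap: these are conduct or reporting provisions, and none takes the response out of ORR. Applying the Appendix 4 window as written leaves it in.

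Two further points limit the claim. The documents do not say whether the trials behind the 23% and 15% benchmarks ended response assessment at new therapy, so an upward bias relative to those benchmarks is not established. A response after stopping could also be a delayed effect of trial product; Protocol 2.8.2 acknowledges delayed responses to immunotherapy.

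**Conclusion.** The gap is real and concerns the primary endpoint: the cut-off used for PFS is absent from every ORR provision, and the stated window ends only at progression or recurrence. It applies only to subjects who switch before RECIST 1.1 progression.

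Under the assumptions above, each cohort's type I error moves modestly above its 0.025 allocation, and the trial-wide rate exceeds 0.05. With no such switching there is no effect. The calculation takes 23% and 15% as the true null rates for responses on trial product.

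A reader might infer that the plan intends to credit another drug's responses to CV301. It does not; they are counted because no rule excludes them. A reader might also infer that the error rate doubles. With 10% switching and 30% responding it reaches 0.050 and 0.064, but 30% is well above the overall-population post-platinum chemotherapy rates in Protocol 2.1 (under 10% for single agents, 11.4%, 13.4%). Nor do the documents support an equal effect at Stage 1.

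This should be fixed, chiefly because one response can decide a cohort.

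**What to change.** In SAP 4.4.5.1, Protocol 9.7.1 and Appendix 4, state that best overall response, under both RECIST 1.1 and iRECIST, uses only assessments made before the start of any new anti-cancer therapy or radiotherapy or surgery to a tumour lesion. For RECIST 1.1 this is in addition to the existing progression cut-off. Subjects without a response by then are non-responders and stay in the denominator. Apply the rule at both the Stage 1 and final analyses. Duration of response has the same silence and could be aligned at the same time.

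The cost is about one sentence in each place. The PFS rule already needs the intervention dates, and sample sizes, boundaries and design error rates are unchanged. The downside is that the reported ORR may be slightly lower, including where a late response was in truth due to trial product.
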